## **10.5 Compensation for Injury**

The Sponsor will adhere to local regulations and guidelines regarding clinical trial compensation to subjects whose health is adversely affected by taking part in the study. The applicable policy for compensation for injury will be described in the master ICF template.

## **10.6 Clinicaltrials.gov**

For purposes of reporting to clinicaltrials.gov, the Sponsor is the responsible party and will provide information regarding this study in accordance with applicable regulations.

## **10.7 Public Disclosure and Publication Policy**

All publication rights are delineated in the Clinical Study Agreement with the Investigator(s).

## **10.8 Amendments**

The protocol may be amended only by the Sponsor.

The IRB must generally be informed of all amendments prior to implementation. In addition, the Investigator must obtain IRB approval for any amendments likely to affect the safety of study subjects prior to implementation.

The Sponsor may implement an amendment prior to IRB notification or approval only in order to eliminate an apparent, immediate hazard to study subjects. In that event, the Sponsor will notify the IRB in writing within 7 calendar days after the implementation.

Amendments, including descriptions and rationales, will be documented in this section of the protocol.

---

## APPENDIX A: SCHEDULE OF EVENTS

Study Event	Visit Number:	--	01	02	03	04	05 to 08	--
	Study Visit:	Screening	Day 1	Day 8	Day 15 (Phone)	Day 29	Months 3, 4, 5, 6 (Phone)	Early Termination
	Window:	-30d		+3d	+3d	±3d	±5d	
Informed Consent		X						
Demographics, Medical History		X		X a				
Concomitant Medications		X	X	X	X	X c	X c	
Physical Exam(s), targeted		X		X a				
Vital Signs		X		X b				
Confirmation of Eligibility		X	X					
Randomization				X				
Study Vaccine Administration				X				
Post-vaccination Observation (at least 30 min)				X				
Issue e-Diary instructions, Ruler, Thermometer; Conduct Training			X					
Review e-Diary Data					X			
AE Evaluation (Solicited and/or Unsolicited)			X	X	X	X	X c	
Clinical Labs d								
Hematology, Chemistry, Urinalysis Tests		X					X	
Pregnancy Tests (Urine or Serum) e		X	X					
HIV EIA, HBsAg, HCV Ab		X						
Serum for Immunogenicity, [REDACTED] (50 to 64 yo only)				X			X	

Refer to  
Section 6.2  
for  
Procedures

Abbreviations: AE = adverse event; HBsAg = Hepatitis B surface antigen; HCV = Hepatitis C virus antibody; HIV EIA = human immunodeficiency virus, enzyme immunoassay;

[REDACTED] SAE = serious adverse event; yo = years old

a Conduct or collect prior to study vaccination (if indicated by updated medical history or change in health status, as applicable).

b Vitals to be taken prior and after study vaccine administration (≥ 30 min).

c New onset of chronic illnesses and SAEs, and associated concomitant medications collected after Day 29.

d All samples collected prior to study vaccine administration.

e Serum pregnancy test at Screening and urine pregnancy test prior to vaccine administration.

OPA	Opsonophagocytic antibody
PCV	Pneumococcal Conjugate Vaccine
PD	Protocol Deviation
PT	Preferred Term

RND	Randomized Population
SAE	Serious Adverse Event
SAF	Safety Population
SAP	Statistical Analysis Plan
SI	International System of Units
SOC	System organ class
TEAE	Treatment Emergent Adverse Event
TLFs	Tables, listings and figures
ULOQ	Upper Limit of Quantification
VAX-24	24-valent investigational pneumococcal conjugate vaccine
WHO	World Health Organization

1. INTRODUCTION AND OBJECTIVES OF ANALYSIS

1.1. Introduction

This statistical analysis plan (SAP) is designed to outline the methods to be used in the analysis of study data to answer the study objective(s). Analysis sets, data handling rules, statistical methods, and formats for data presentation are provided. The statistical analyses and summary tabulations described in this SAP will provide the basis for the results sections of the clinical study report (CSR) for this trial.

Analyses planned for the Data Monitoring Committee (DMC) meeting at the end of Phase 1 will be described in a separate document.

1.2. Objectives

The primary objectives are:

- To evaluate the safety and tolerability of a single injection of VAX-24 at three dose levels administered to healthy adults 18 to 64 years of age.
- To compare the safety of VAX-24 to that of PCV20 administered to two control groups: 1) subjects 18 to 49 years of age receiving PCV20, and 2) subjects 50 to 64 years of age receiving PCV20.

The secondary objectives are:

- Safety: To assess laboratory value abnormalities and/or potentially clinically significant laboratory values following VAX-24 at 3 dose levels compared to control groups receiving PCV20 for subjects aged 50 to 64 years.
- Immunogenicity: To assess the induction of antibody responses by VAX-24 dose levels compared to control groups receiving PCV20 for subjects aged 50 to 64 years.

The exploratory objective is to further characterize the immune response to PCVs in 100 subjects 50 to 64 years of age. Serum samples may also be used for further characterization and validation of clinical assays

2. STUDY DESIGN

2.1. Introduction

This Phase 1/2a parallel-group, randomized, observer-blind study is to be conducted in two populations of healthy adults, 18 to 49 years of age and 50 to 64 years of age. Subjects will be randomly assigned in a 1:1:1:1 ratio to receive either VAX-24 at one of three dose levels or the active comparator.

A Phase 1 cohort of 64 subjects (16 for each VAX-24 dose group and 16 for the comparator group) aged 18 to 49 years will be enrolled initially. Subjects will receive VAX-24 or PCV20 on Day 1. All subjects will have safety labs analyzed at Baseline and 28 days post-vaccination (Day 29). Solicited adverse events (AEs) will be collected for 7 days post-vaccination and unsolicited safety information for 28 days post-vaccination, with serious adverse events (SAEs), new onset of chronic illness (NOCI) and medically attended adverse events (MAAEs) collected up to 6 months post-vaccination. A defined safety review of data (solicited and unsolicited AEs, and SAEs) through 7 days post-vaccination will occur by an independent DMC before proceeding with enrollment of the remaining subjects, adults 50 to 64 years of age.

Subjects in the 50-to-64-year-old group will receive VAX-24 or PCV20. Solicited and unsolicited AEs will be collected similarly to the subjects aged 18 to 49 years described. All subjects in this age group will have blood samples drawn for immunogenicity analysis (Opsonophagocytic antibody (OPA) and Immunoglobulin G (IgG)) at Days 1, 29.

Approximately 100 of the 800 subjects from 50 to 64 years of age will be consented for collection of additional blood samples (up to 32 mL per draw) by a limited number of clinical sites; subjects will have blood samples drawn at Days 1 and 29 to further characterize the immune response to PCVs.

The schedule of assessments is in Appendix A, further details available in the study protocol.

2.2. Sample Size and Power

Sample size is not driven by statistical assumptions.

For subjects 18 to 49 years of age, with 16 subjects, events that occur at a frequency of 15% or more will be detected with at least 92% probability and events that occur at a frequency of 10% or more will be detected with 81% probability. Therefore 16 subjects in each treatment group are proposed as the basis for the number of subjects in whom to conduct the first safety assessment.

For subjects 50 to 64 years of age, a total of 800 subjects will provide sufficient information to assess safety and immunogenicity. The sample size will also be adequate to plan future studies.

2.3. Randomization Methodology

[figure not shown]
For the Phase 1 Cohort (18-to-49-year-old age range), a total of 64 subjects are planned to be randomized in a 1:1:1:1 allocation ratio i.e.16 subjects in each VAX-24 dose arm and 16 in the Prevnar group. There will be no stratification factors.

For the Phase 2 Cohort (50-to-64-year-old age range), a total of 800 subjects are planned to be randomized in a 1:1:1:1 allocation ratio i.e.200 subjects in each VAX-24 dose arm and 200 in the Prevnar group. The randomization will be stratified using the following age groups as a stratification factor:

- Age ≥ 50 and ≤ 59 years old
- Age ≥ 60 and ≤ 64 years old

2.4. Stopping Rules

The rules governing the halting or stopping of the study vaccine administration at any time during the study are defined by age groups 18 to 49 and 50 to 64 years in the Phase 1 and Phase 2 segments of the clinical study, respectively. During the vaccination period(s), if any of the stopping rules are triggered, no further administration of study vaccine(s) will occur until safety data are reviewed by the DMC in communication with the Sponsor Medical Director and the Investigator at the site where the event occurred, as needed. Study dosing may be resumed if the DMC determines it is safe to proceed with no modifications or with modifications to the protocol plans.

Enrollment may be resumed following review of available safety data by the Sponsor.

The study is planned to be completed after all subjects have completed the Day 180 (Month 6) visit (or Early Discontinuation, as appropriate), all necessary safety follow-up has been completed, and all data have been monitored and queries have been resolved. The Sponsor reserves the right to terminate the study prior to the planned study completion.

2.5. Blinding

This is an observer-blind study in which all participants, Investigators, and study personnel involved in the conduct of the study, including data management, are blinded to treatment assignment except for:

- Unblinded independent statisticians who will prepare and have access to the randomization code
- Third-Party Vendors (Interactive Response Technology and Supply Management)
- Unblinded pharmacist or designee at site who will prepare Investigational Product (IP)
- Unblinded Administrator at site who will dispense IP
- Unblinded Clinical Research Associate/Study Monitor who will monitor pharmacy
- Unblinded Lead Clinical Research Associate and Clinical Trial Assistant who will review the unblinded Clinical Research Associate/Study Monitor's reports and manage IP supply orders and inventory
- Unblinded Sponsor QA Consultant(s)

Although unblinded to treatment assignment, none of the above roles will have access to unblinded summaries of immunogenicity or safety data.

The following personnel will have access to unblinded data, including individual treatment assignment and individual immunogenicity data, in order to discharge their roles for data analysis and review during the planned Interim Analysis at the end of Phase 1 and the Day 29 Analysis:

- The unblinded statistical programming team, the unblinded data manager, and independent support statistician who will prepare unblinded reports for DMC meetings
- The DMC members who will review unblinded data reports
- The unblinded programming team and the unblinded statistician who will prepare the unblinded report for Day 29 Analysis
- Unblinded Sponsor Reviewer Consultant

Other than the above-mentioned personnel, all other individuals involved in the study conduct, statistical analysis and reporting will remain blinded to individual treatment assignments and individual immunogenicity data until official study unblinding at the end of the study.

Sponsor personnel and limited blinded personnel will become treatment-group unblinded and have access to immunogenicity and safety summaries after the interim database lock (iDBL) for the Day 29 Analysis, as described in Section 2.7.

2.6. Interim Analyses

A defined safety evaluation will be conducted for the Phase 1 cohort of subjects aged 18 to 49 years, based on the safety data collected through Day 8. The results will be reported to the DMC by treatment group preserving the double-blind status on the subject level, unless the DMC requests unblinded individual treatments. If the interim safety analysis supports and DMC concludes that no safety concerns exist, the study will resume enrollment of subjects aged 50 to 64 years.

For further information including the tables, listings and figures (TLF) to be provided for the DMC review, please refer to the VAX24-101 DMC Charter and associated DMC Mock tables, listings and figures (TLFs) document.

2.7. Schedule of Analyses

Statistical analyses described in this SAP will be carried out in two stages:

- Day 29 Analysis:

An interim DBL will occur after all subjects have completed the Day 29 visit and their data up to Day 29 visit have been cleaned. Primary Safety and Immunogenicity endpoints will be produced by programmers with the support of an unblinded statistician. The exact scope and list of outputs for the Day 29 Analysis will be decided prior to the iDBL by the Sponsor and documented in separate TFL shells documents. The results by treatment group will then be available to Sponsor and other study personnel. All blinded personnel, as indicated in Section 2.5, will remain blinded to individual treatment until final database lock. To that effect, no listing of individual data will be part of the Day 29 Delivery and the remaining outputs will be reviewed first by the Unblinded Sponsor Reviewer to assess potential unblinding. The Unblinded Sponsor Reviewer will redact any results by treatment group that may be unblinding and provide the redacted outputs to the wider blinded team.

- Final Analysis:

The final DBL will occur when all subjects have completed the study, and all data through the last Month 6 visit have been cleaned. Individual Treatment unblinding will be available to all study personnel after the final DBL. The Final Analysis will include all analyses described in this SAP. A single completed Clinical Study Report (CSR) will summarize safety findings through Month 6 for all subjects and immunogenicity data for subjects 50 to 64 years of age.

3. STUDY ENDPOINTS

3.1. Efficacy Variables

No Efficacy endpoint has been defined for this study.

3.2. Safety Variables

Safety assessments performed during the study included solicited AE up to Day 8 and monitoring of unsolicited adverse events, physical examinations, measurement of vital signs, clinical laboratory evaluations including hematology, serum chemistry, and urinalysis.

The primary endpoints are:

- Percentage of subjects reporting solicited local reactions within 7 days after vaccination (redness, swelling, and pain at injection site) in each age group.
- Percentage of subjects reporting solicited systemic events within 7 days after vaccination (fever, headache, fatigue, muscle pain, and joint pain) in each age group.
- Percentage of subjects reporting unsolicited AEs within 1 month after vaccination in each age group.
- Percentage of subjects reporting SAEs, NOCIs, and MAAEs within 6 months after vaccination.

The secondary endpoint related to Safety assessments is:

- Percentage of participants with laboratory value abnormalities and/or potentially clinically significant laboratory values at 1 month after vaccination.

3.3. Immunogenicity Variables

Immunogenicity samples will be collected for subjects aged 50 to 64 years only at Day 1, Day 29 and at the Early Discontinuation Visit for subjects discontinuing before Month 6 visit.

Immunogenicity parameters to be determined include OPA and IgG assays.

The secondary endpoints related to Immunogenicity assessments are:

- 24 VAX-24 Pneumococcal serotype-specific OPA geometric mean titer (GMTs) at 1 month after vaccination (Day 29).
- 24 VAX-24 Pneumococcal serotype-specific IgG geometric mean concentration (GMCs) at 1 month after vaccination (Day 29).

The exploratory endpoints are all evaluated at 1 month after vaccination (Day 29):

- Geometric Mean Fold Rise (GMFR) in serotype-specific OPA

- GMFR in serotype-specific IgG
- Percentage of participants with GMFR ≥ 4 in serotype-specific OPA
- Percentage of participants with GMFR ≥ 4 in serotype-specific IgG
- Comparison of geometric mean ratio (GMR) of serotype specific OPA and IgG
- Proportion achieving an OPA titer of at least the serotype-specific Lower Limit of Quantitation (LLOQ) of the assay
- Reverse cumulative distribution curves for OPA titers

4. ANALYSIS SETS

4.1. Analysis Set Definitions

The following Analysis sets will be evaluated and used for presentation and analysis of the data:

- **Screened Population**: Includes all screened subjects who provided informed consent and were assigned a study subject number, regardless of whether the subject was randomized or not. This population will be used to account fully for subject disposition, starting with the informed consent. The screened population will not be analyzed as such but will be available in the clinical database.
- **Randomized Population (RND)**: Includes all subjects from the Screened Population who consented, provided demographic and other Baseline Screening measurements, and were randomized. Each subject will be analyzed as randomized.
- **Exposed Population (EXP)**: Includes all subjects from the Screened Population who received at least one study vaccine administration. Each subject will be analyzed as treated.
- **Safety Population (SAF)**: Includes all subjects in the Exposed Population but excluding subjects lost to follow up at Day 1 reporting no solicited or unsolicited AEs. Each subject will be analyzed as treated.
- **Immunogenicity Evaluable Population (IEP)**: Includes all subjects in the Exposed Population who:
 - Had no major protocol deviation that would impact immunogenicity assessment or other reason to be excluded as defined prior to unblinding or analysis.
 - Had not received a prohibited medication or vaccine. Identification of subjects receiving prohibited medications will be done via a medical review from the Sponsor of a listing of all concomitant medications.
 - Provided evaluable serum sample results for baseline, the relevant post-vaccination time points, and within the required time frames:
 - Baseline: Day 1 or within 30 days before first study vaccine administration
 - Day 29: Day 26 through Day 34, inclusive

Each subject will be analyzed as treated.

“As randomized” means according to the vaccine regimen to which the subject was randomized, while “as treated” means according to the vaccine regimen a subject received, rather than the vaccine regimen to which the subject may have been randomized.

The RND will be used for the analysis of exposure.

The SAF will be the primary set for the analysis of the safety parameters.

The IEP will be the primary set for the immunogenicity analysis, with the EXP set as supportive.

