### 3.3 Estimated Study Duration

The Screening period is 30 days, treatment and observation period is from Day 1 to Day 29, and the follow-up period is through Day 180 (6 months from study vaccination). The maximum possible study duration for an individual is 210 days.

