## 5.10 Acute Observation

The subject will be monitored by blinded study staff for signs of an acute adverse reaction and vital signs will be obtained at least 30 minutes after injection. If a subject reports any symptom collected as Solicited AEs for this study, the blinded study staff will advise them to record the details in their electronic diary at the end of their day.

Allergic reactions to the study vaccine are possible; therefore, appropriate drugs and medical equipment to treat acute anaphylactic reactions must be immediately available and a medically qualified study team member trained to recognize and treat anaphylaxis must be present in the clinic during the entire post-dosing monitoring period.

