### **5.19 Early Discontinuation**

An individual subject is considered to undergo Early Discontinuation if the subject stops study participation before the Day 180 visit.

An enrolled subject may voluntarily withdraw consent for further participation at any time before the Day 180 visit. The Investigator will request (but cannot require) such subjects to provide the reason(s) for withdrawal of consent and to undergo an Early Discontinuation visit.

In addition, the Investigator, at his or her discretion, may withdraw a subject from further participation in the study. Criteria for withdrawal by the Investigator include:

- Noncompliance with the protocol
- Pregnancy
- Immediate hypersensitivity reaction associated with a study injection
- Loss to follow-up – requires documentation of at least 3 unsuccessful attempts to contact the subject. Lost to follow-up will be determined after the date of the subject's projected last visit.
- Other reason(s) which, in the opinion of the Investigator, indicates that continued participation in the study is not in the best interest of the subject.

The Investigator or designee must report any early discontinuation for safety reasons to the Medical Monitor or designee within 24 hours of discontinuation. Additional information regarding ongoing AEs may be provided as a follow-up report.

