### 9.4 Populations for Analysis

**Randomized Population:** All screened subjects who provide informed consent, provide demographic and other Baseline Screening measurements, are randomized, and are assigned a study subject ID (number). Each subject will be analyzed as randomized (ie, according to the vaccine regimen to which the subject was randomized).

**Exposed Population:** All subjects who receive at least one study vaccination.

**Safety Population:** All subjects in the Exposed Population who provide safety assessment data. This generally includes any subjects not lost to follow-up at Day 1, as they will be at risk for reporting an SAE. Each subject will be analyzed as treated (ie, according to the vaccine regimen a subject received, rather than the vaccine regimen to which the subject may have been randomized).

**Immunogenicity Evaluable Population:** For this Phase 1/2 study, the immunogenicity population will be analyzed as treated (ie, according to the vaccine regimen a subject receives, which may be different from the vaccine regimen to which the subject is randomized in the case of treatment errors). The Phase 1 subjects aged 18 to 49 years are not included in this population.

The Immunogenicity Evaluable Population (IEP) includes all subjects in the Exposed Population who:

- Have no major protocol deviation that would impact immunogenicity assessment or other reason to be excluded as defined prior to unblinding or analysis.
- Have not received a prohibited medication or vaccine.
- Provide evaluable serum sample results for baseline, the relevant post-vaccination time points, and within the required time frames:
  - Baseline: Day 1 or within 30 days before study vaccine administration
  - Day 29: Day 26 through Day 34, inclusive

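### The SAP drops vaccinated subjects lost at Day 1 from the Safety Population only if they reported no AE, so the denominator depends on the outcome; nor does it say how such loss is identified at the Day 29 lock

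*SAP*

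**What the plan says.** SAP 4.1 builds the Safety Population from the Exposed Population with one exclusion: "Includes all subjects in the Exposed Population but excluding subjects lost to follow up at Day 1 reporting no solicited or unsolicited AEs". Subjects are analysed as treated, and the same section adds: "The SAF will be the primary set for the analysis of the safety parameters". SAP 6.5 produces all safety summaries on this set.

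Protocol 9.4 defines it differently: "All subjects in the Exposed Population who provide safety assessment data". It then explains: "This generally includes any subjects not lost to follow-up at Day 1, as they will be at risk for reporting an SAE". Neither sentence mentions whether an AE was reported. SAP Section 7 states that nothing has changed from the protocol's planned analyses.

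On Day 1 each vaccinated subject is observed by blinded staff, and "vital signs will be obtained at least 30 minutes after injection" (protocol 5.10). Protocol 6.1.2 also schedules an AE evaluation after the injection.

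On when loss is established, protocol 5.19 says: "Lost to follow-up will be determined after the date of the subject's projected last visit". It also requires at least three failed contact attempts. The last visit is at Day 180 (protocol 3.3 and 5.18). For the Day 29 Analysis, SAP 2.7 says: "An interim DBL will occur after all subjects have completed the Day 29 visit", with data cleaned to that visit.

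**The concern.** An analysis set should be fixed by exposure and data availability, not by the result being measured. Here the result decides. A Day 1 loss with an AE counts in both numerator and denominator; a Day 1 loss without one leaves the denominator. The percentages affected are primary endpoints.

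The rule can also discard usable data. An AE-free subject who is vaccinated, observed, has vital signs taken and is never seen again would normally have safety assessment data in the protocol's sense. SAP 6.5.3 summarises the change in vital signs from before to after vaccination on Day 1. That subject has complete data for this table and is left out of it for having no AE.

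The second issue is timing. The exclusion needs to know who was lost at Day 1. The SAP gives no definition of its own, and the status in protocol 5.19 is assigned only after Day 180. A subject treated as lost at the Day 29 lock could be reached at a Month 3 to 6 call and re-enter the set. The same Day 29 endpoint could then be reported with two denominators.

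**Working it through.** **Inputs.** Arm sizes are 16 (age 18 to 49) and 200 (age 50 to 64) from protocol Table 4, and at least 25 per arm for age 60 to 64 from protocol 5.8. The documents give no Day 1 loss rate and no expected AE rates, so the losses and event counts below are assumptions.

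**The plan's own figure.** Protocol 9.1 and SAP 2.2 give the chance of seeing at least one event in 16 subjects. From 1 − (1 − p)^16, p = 0.15 gives 92.6% (stated: at least 92%) and p = 0.10 gives 81.5% (stated: 81%). Both reproduce. The SAP rule removes no subject with an event, so its effect is on percentages, not on whether an event is seen.

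**Direction within an arm.** Let n be exposed, L lost at Day 1, a of those L with an AE, and x subjects with an AE among the other n − L.

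- Keep all exposed: (x + a)/n
- SAP rule: (x + a)/(n − L + a)
- Drop all Day 1 losses: x/(n − L)

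Since a ≤ L, the SAP denominator is at most n, so the SAP figure is never below the keep-all figure. Write m = n − L. Then (x + a)/(m + a) − x/m has the sign of a(m − x), which is never negative, so the SAP figure is never below the drop-all figure either. With no events in the arm all three are zero.

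Example with n = 200, L = 10, a = 2, x = 40:

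- Keep all: 42/200 = 21.0%
- Drop all: 40/190 = 21.05%
- SAP rule: 42/192 = 21.9%

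**Size, with only AE-free Day 1 losses dropped.**

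| Arm | Subjects with AE | All exposed | Dropped | SAP rule |
|---|---|---|---|---|
| 200 | 40 | 20.0% | 1 | 40/199 = 20.1% |
| 200 | 40 | 20.0% | 4 | 40/196 = 20.4% |
| 200 | 40 | 20.0% | 10 | 40/190 = 21.1% |
| 25 | 5 | 20.0% | 1 | 5/24 = 20.8% |
| 16 | 8 | 50.0% | 1 | 8/15 = 53.3% |
| 16 | 8 | 50.0% | 2 | 8/14 = 57.1% |

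**Between arms.** Take 40/200 in both arms. Dropping four AE-free subjects from the VAX-24 arm only gives 20.41 − 20.00 = +0.41 points. Dropping them from the PCV20 arm only gives −0.41.

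**Which tables.** SAP 6.5.1.1 already limits solicited AE tables to subjects with some diary observation, so most Day 1 losses are out of them anyway. An exception is a Day 1 loss whose only diary entry is all zeros. Day 29 laboratory percentages use non-missing values (SAP 6.2.6). The rule therefore acts mainly on unsolicited AEs, SAEs, NOCIs and MAAEs, and on the Day 1 vital-sign table.

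**Timing.** Day 180 is 180 − 29 = 151 days after Day 29. Assume uniform enrolment over D days and C days of cleaning after the last Day 29 visit. The share of subjects past Day 180 at the lock is max(0, (D − 151 + C)/D).

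- D = 60 or 90, C from 0 to 60: 0%
- D = 150: 0% (C = 0) to 59/150 = 39% (C = 60)
- D = 180: 29/180 = 16% (C = 0) to 89/180 = 49% (C = 60)

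Under these assumptions the protocol 5.19 status is missing at the Day 29 lock for at least half of the subjects, and for all of them if enrolment is quick.

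**The case against.** The protocol itself contemplates leaving out Day 1 losses, since its explanatory sentence speaks of subjects not lost at Day 1. The SAP can be read as putting that into practice while making sure that no reported event is thrown away, which is a cautious choice for safety. Keeping a subject seen only on Day 1 in a 28-day or 6-month denominator also treats unobserved time as event-free, which pulls the percentage down. Few vaccinated subjects should be lost on Day 1 with no later contact, and SAP 6.3.1 would show any exclusion in the analysis-set counts and listings. SAP 6.2.1 plans formal testing only for immunogenicity.

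Much of this stands. It limits the size of the problem and rules out a claim about true risk. It does not justify the AE condition: an intention to keep reported events is met equally well by a rule that keeps everyone with safety data, and protocol 9.4 has no such condition.

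A reader might infer that the rule cannot be applied at all at the Day 29 Analysis. The documents do not support that. Loss at Day 1 can be read as no contact after Day 1, which visit and call records would show at the lock, and some early enrollees may already be past Day 180. What is missing is a statement of which reading applies.

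**Conclusion.** The point holds as a correctable flaw in the definition of the primary safety set. Among subjects lost at Day 1, membership depends on the outcome; this departs from protocol 9.4 and is not declared. The direction within an arm is certain relative to keeping all exposed subjects or dropping all Day 1 losses: equal or higher, never lower. The size is probably small, about 0.1 point per dropped subject at 40/200. It is about 3 points at 8/16, so the age 18 to 49 arms are the most sensitive. These sizes rest on assumed losses and event counts.

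A reader might go further and infer that AE rates are biased upward, or that the comparison is tilted against VAX-24. Neither follows. The comparison here is with other denominators, not with true risk, and the between-arm difference can move in either direction, depending on which arm loses more AE-free subjects.

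The timing gap is one of specification: the SAP does not say how Day 1 loss is identified at the Day 29 lock, and the protocol's status is not yet available for subjects who have not passed Day 180. Denominators for the same endpoint could therefore differ between the two analyses.

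**What to change.** Change SAP 4.1 only. Suggested wording: *Safety Population: every subject in the Exposed Population with any safety assessment recorded after vaccination, including the Day 1 observation and vital signs, whether or not an AE was reported; analysed as treated.* In practice this is almost all of the Exposed Population.

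State that the same data-based rule applies at the interim and the final lock, so that membership does not wait on the protocol 5.19 status. Leave the existing diary-observation rule for solicited AE tables as it is. A line in SAP Section 7 can record how the protocol's criterion is being read.

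This returns to the protocol's criterion, so no protocol amendment and no new data are needed. The cost is that a few denominators become slightly larger and include subjects with little follow-up, whose unobserved time counts as event-free. The disposition table and listings already planned will show how many there are.
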